The THC Urine Dipstick Test is an immunochromatography device based on the principle of competitive immunoassay. The nitrocellulose membrane of the dipstick is immobilized with THC-protein conjugate on the test zone (see Figure 2). Antibodies against THC, which have been conjugated with colloidal gold, are impregnated on a porous pad overlapping the bottom end of the membrane. When the sample pad of the dipstick is dipped into the urine sample to perform the test, by capillary attraction, the urine will flow through the porous pad towards the other end of the assay strip. The antibody-gold conjugate dissolved by the urine sample will flow with the liquid front-end. In the absence of THC, the antibody-gold conjugate will bind to the immobilized drug conjugate causing a visible red band to appear at the test zone. However, when a sufficient concentration of THC (>50 ng/mL) is present in the urine sample, the THC in urine will bind with the antibody and saturate the binding capacity of the antibody-gold conjugate, thus, no visible band will appear at the test zone.

Possible Results: NEGATIVE: If there is no THC present in urine, there will be a rose-color bands appearing on both the control and the test section. POSITIVE: A positive result is observed when there is a control line and no test line and indicates a minimum THC concentration of 50 ng/mL. At concentrations less than 50 ng/mL, there may be weak signal appearing at the test line area. INVALID: If there is no rose-color band visible in the control window, then the test result is invalid. (Source: Acro Biotech Inc., Rancho Cucamonga, CA, www.acrobiotec.com)

Figure 2. Dipstick Test Results

Subject Compensation

Subjects will receive compensation at each clinic visit for their time and effort. Subjects will be paid \$25 for Screening Visit 1 and \$25 for Screening Visit 2. For each follow-up visit they attend, they will be compensated \$20 for their time, for completing study procedures and to cover transportation costs. Subjects will also complete the Balloon Analogue Risk Task (BART) twice during the study. The average compensation a subject can earn from this task is \$35. The subject will also be eligible for a study bonus upon study completion: \$30 for attending W5 and \$50 for missing no more than 1 follow-up clinic visit (must not be Week 4).

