- *Behavioral Inhibition/Activation scales (BIS/BAS)*: 20-item form is commonly used to study externalizing tendencies (Carver and White, 1994). Investigators in Project II have used this instrument with success.
- *Barratt Impulsiveness Scale (BIS)*: 30-item self-report measure of self-control (Patton et al 1995). Doran and colleagues (2004) demonstrated that impulsivity, as measured with this item, was a predictor of smoking relapse.
- *Brief Self Control Scale (BSCS)*: This item consists of 13 questions rated on a 4-point scale from “very true” to “very false” on items reflecting the ability to control problematic behaviors (Tangney et al 2004).

The *Impulsivity Tasks* represent two forms of impulsivity, 1) impaired cognitive inhibitory mechanisms, and 2)

deficits in motor inhibitory mechanisms. “Delay discounting” entails higher-level cognitive inhibitory processes that may characterize the behavior of individuals who are drug dependent (Bickel and Marsch, 2001) tobacco users (Baker et al. 2003), cocaine users (Monterosso et al, 2001), other drug users (e.g. Vuchinich and Simpson, 1998; Kollins, 2003) and pathological gamblers (Dixon et al, 2003). The following items will be completed at Screening Visit 2 and Week 4.

- **Delay Discounting Task:** Developed by de Wit and colleagues (Richards et al, 1999), delay discounting refers to the reduction in value of a reward over time relative to its immediate worth. One’s discount rate, also known as a time preference, is a measurable individual difference and involves a series of choices (e.g. Petry and Casarella, 1999): one option is an immediate payment (e.g. \$1); the second option is a larger payment (e.g. \$50) after a delay (e.g. 6 hours to 25 years). Titrating the payment amounts at each delay interval allows the identification of points of indifference (the point at which the subject switches from choosing the immediate to the larger reward at a given delay interval). We additionally included a probability discounting condition to measure risk aversion in addition to time preference (Richards et al, 1999).

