- **GoStop Task:** This task measures response inhibition. A series of five-digit numbers are presented on a computer monitor at a rate of 500ms for ever two seconds. Subjects are instructed to click the mouse button when the number they see is identical to the previous number. Half of the numbers change color from black to red at 50, 150, 250 and 350. Subjects are instructed to respond to the matching number only when the displayed number is black. The primary outcome of this task is the percent of inhibition failures for the 150ms delay (Dougherty et al 2008). This item has been successfully used to assess tobacco dependence and smoking behavior (Billieux et al 2010).
- **Balloon Analogue Risk Task (BART):** This task, with 30 replications/session, is a measure of risk-taking. It involves displaying a small balloon on a computer screen. Each “pump” to inflate the balloon accumulates five cents, with each pump potentially breaking the balloon. The average pumps to the breaking point is 64. To ensure attentive responding, subjects will receive the actual amount of money accrued on this task. The primary outcome on this task was the number of exploded balloons divided by the number of trials (Lejuez et al, 2002).
- **Immediate Memory Task / Delayed Memory Task (IMT/DMT):** This task is a continuous performance task that has two phases. First, the IMT displays a series of five-digit numbers in on a computer monitor for 500 ms followed by a blank screen 500 ms. Subjects click the mouse button whenever an identical number is displayed. Next, the DMT requires the subject to remember a five-digit number and compare it to another that is presented 3.5 seconds later. During the 3.5 interval subjects are presented with a distracter (12345) and told to ignore it. The primary outcome of this task is the IMT/DMT ratio which is defined as the proportion of commission errors to correct detections (Mathias et al 2002). This item is included as it we have used it in prior studies to identify menstrual phase differences in impulsivity and attention (see Preliminary Studies B.2.1.), and therefore is expected to be sensitive to the group differences in sex and progesterone.

Independent Measures (sex, randomization, and serum progesterone):

Sex will be collected via self-report on the Demographics form completed at Screening Visit 1.

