Addressing Hypothesis 1a: An unadjusted assessment of the treatment effect will come from a linear model of percent reduction in marijuana use on randomized treatment assignment, separately by sex. **Hypothesis 1b:** A linear model including both males and females will be used to estimate the overall gender effect on percent reduction in marijuana use. **Hypothesis 1c:** A linear model including both males and females will be used to estimate the association of serum progesterone with percent reduction in marijuana use; we will separately consider baseline progesterone, cumulative progesterone (summed over weeks 0-4), and week 4 progesterone.

Addressing Hypothesis 2a: A linear model including both males and females will be used to estimate the association of impulsivity with percent reduction in marijuana use. **Hypothesis 2b:** A linear model including both males and females will be used to estimate the interaction between baseline impulsivity and baseline serum progesterone on percent reduction in marijuana use.

Missing data plan: Quality assurance plans are described below. The primary outcome analysis will be carried out using two parallel models: one model will exclude subjects for whom we were unable to obtain a week 4 TLFB or urine THC. Since 'missing at random' is a strong statistical assumption to make, we will also carry out a parallel model that uses multiple imputation of the week 4 TLFB and urine THC based on an individual's previous visits' TLFB and urine THC levels. We will also examine whether persons missing their week 4 visit differed in their baseline characteristics or treatment assignment from persons not missing their week 4 visit.

Power: This is a pilot study to generate data to potentially motivate and justify a future fully-powered study of PRO and marijuana use. This study will estimate magnitude and direction of treatment effects and associations with impulsivity (sex-specific and overall). Hence, no power calculations are provided.

Data Safety and Monitoring Plan, Board, and Administration.

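### Scoring the BART by the share of exploded balloons adds avoidable chance noise, which weakens any BART-based estimate in the exploratory and adjusted analyses

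*Combined protocol and SAP*

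**What the plan says.** Under Study Measures, the BART entry sets the design and the score. "This task, with 30 replications/session, is a measure of risk-taking". Each pump "accumulates five cents, with each pump potentially breaking the balloon". "The average pumps to the breaking point is 64". To keep participants attentive, "subjects will receive the actual amount of money accrued on this task". The score is then fixed: "The primary outcome on this task was the number of exploded balloons divided by the number of trials". No other BART score is named.

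On timing, the impulsivity-task section says: "The following items will be completed at Screening Visit 2 and Week 4". The baseline value therefore comes from Screening Visit 2. Subject Compensation puts average BART earnings at $35, and the total there counts $70 for two sessions, so $35 is a per-session figure.

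In the Analysis Plan, Hypothesis 2a is a linear model to "estimate the association of impulsivity with percent reduction in marijuana use". Hypothesis 2b uses the interaction of baseline impulsivity with baseline serum progesterone. Baseline impulsivity measures are also listed among possible adjusting covariates. None of these places says which impulsivity instrument is meant.

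**The concern.** The exploded share reduces each balloon to a yes/no result. Two participants with the same willingness to pump will get different shares through the luck of the break points. A predictor measured with error biases its regression slope toward zero, and careful reporting does not remove that bias. The stated purpose of this pilot is to estimate the size and direction of associations with impulsivity, so a biased estimate matters even though no power is claimed. With about 40 analysable participants there is little information to waste. A covariate measured with error also adjusts less completely.

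The task already yields a finer reading, namely how far the participant pumped on balloons that did not burst.

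**Working it through.** The documents state no reliability for this score, so there is no figure to reproduce. The check calibrates the task to the plan's own payment figures and then varies what is not stated.

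**Inputs from the documents.** 30 balloons per session, $0.05 per pump, mean break point 64, average winnings $35 per session.

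**Assumed, because not stated.** Burst balloons forfeit their money. Break points are uniform on 1-128 (mean 64.5), with a constant hazard of 1/64 as an alternative. Break points are independent between participants, with one common sequence as an alternative. Between-person SD of target pumps is 8-18 and within-person (balloon-to-balloon) SD is 0-15.

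**Calibration, uniform break points.**
- Credited pumps per balloon: 35 / (30 × 0.05) = 23.3.
- For a constant target of k pumps, k(1 − k/128) = 23.3 gives k = 30.7. The other root, about 97 pumps, is implausible.
- Burst probability p = 30.7/128 = 0.24, or 7.2 bursts in 30.

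**Chance error in one participant's share.**
- SD = √(0.24 × 0.76 / 30) = 0.078, which is 2.3 bursts or 0.078 × 128 ≈ 10 pumps.
- The 95% half-width is 1.96 × 0.078 = 0.15, about 20 pumps around a typical target of 31.

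**Reliability of the share.** With Vb = (SD/128)² and Ve = (p(1 − p) − Vb)/30, reliability is Vb/(Vb + Ve). A correlation shrinks by its square root; a slope on the score shrinks by the reliability itself.

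| Between-person SD (pumps) | Reliability | Correlation factor |
|---|---|---|
| 8 | 0.40 | 0.63 |
| 10 | 0.51 | 0.71 |
| 12 | 0.60 | 0.78 |
| 15 | 0.71 | 0.84 |
| 18 | 0.78 | 0.89 |

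Chance makes up half the variance when Vb = Ve, that is at SD = 128 × √(0.24 × 0.76 / 31) ≈ 10 pumps.

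**Constant hazard of 1/64.** Solving k(63/64)^k = 23.3 gives k ≈ 61 and p ≈ 0.61, and the half-variance point moves to between 14 and 15 pumps. This is an edge case: the most a constant target can earn is about 30 × 0.05 × 63.5 × e⁻¹ = $35.04, so an average of $35 would need near-optimal play.

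**Simulation of both scores.** Correlation with the true target over the SD ranges above; the common-sequence row averages over simulated sequences:

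| Break points | Exploded share | Mean pumps, unexploded balloons |
|---|---|---|
| Independent, uniform 1-128 | 0.60-0.88 | 0.92-1.00 |
| One common uniform sequence | 0.79-0.97 | 0.93-1.00 |
| Independent, constant hazard | 0.46-0.79 | 0.87-1.00 |

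The pump score was the better of the two in every setting.

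**What this does to an estimate.** Take a true correlation of 0.40 (illustrative only). With independent uniform break points the share would show on average 0.40 × 0.60 = 0.24 to 0.40 × 0.88 = 0.35. The pump score would show 0.40 × 0.92 = 0.37 to 0.40.

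**Can the pump score be obtained?** If burst balloons pay nothing, mean pumps on unexploded balloons = winnings / ($0.05 × number unexploded). At $35 and p = 0.24 this is 35 / (0.05 × 30 × 0.76) = 30.7, which returns the calibrated target.

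**The case against.** The strongest reply is that the size of the loss rests on quantities absent from the documents: the between-person SD, the break-point distribution, and whether all participants see the same sequence. That stands. A common sequence alone lifts the share's correlation to 0.79-0.97. A reader might infer that the share is mostly chance or that Hypothesis 2a is heavily attenuated. Neither is shown, because under uniform independent break points chance is the minority of the variance once the between-person SD exceeds about 10 pumps.

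A reader might also infer that pump counts are already recorded. No section says so. Paying actual winnings implies a session total, and deriving mean pumps from it needs the forfeiture rule, which is implied but not stated.

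The link to the hypotheses is also loose. The second aim is exploratory and refers to impulsivity in general. The BART is one of seven instruments, alongside the BIS/BAS, Barratt, Brief Self Control Scale, delay discounting, GoStop and IMT/DMT. Only BART-based versions of the analyses are touched.

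The pump score is not perfect either. It drops burst balloons, which tend to be the high-pump ones, so it somewhat compresses the scale, and a more reliable score need not be a better predictor of marijuana reduction. Finally, the background plans a comparison with the parent nicotine study, which is a fair reason to keep the existing score available.

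These points limit the wording and the weight. None makes the exploded share the more precise measure of willingness to pump.

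**Conclusion.** The point holds as a low-cost improvement. The stated score adds avoidable break-point noise, and mean pumps on unexploded balloons tracked the true target better under every assumption tried: 0.87-1.00, against a range for the share that runs from 0.46 (constant hazard, smallest between-person SD) to 0.97 (common sequence, largest SD). In the central case of independent uniform break points, the share's reliability is about 0.4-0.8. The direction is firm. The size is conditional on between-person SDs of 8-18 pumps, within-person SDs of 0-15 and the break-point rule, all of which are assumptions.

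The effect is confined to exploratory BART analyses and to covariate adjustment that uses the BART. The unadjusted primary comparison of progesterone with placebo does not use the score.

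**What to change.** In the BART entry and the Analysis Plan, pre-specify mean pumps on unexploded balloons as the BART score for Hypotheses 2a and 2b and for any adjusted model that includes the BART. Report the exploded share beside it, for comparability with the parent nicotine study. Take the score from stored pump counts if the task software keeps them; otherwise compute session winnings / ($0.05 × number of unexploded balloons), after confirming that burst balloons forfeit their money. State also how break points are generated and whether all participants share one sequence.

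The cost is a few lines of text and a second BART score to report. No new visit or task is needed, provided that either the pump counts or the session winnings and burst counts are held.

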Inclusion: Males 18-60 years old, females 18-50 years old, stable physical and mental health, self-report Timeline Follow-Back (TLFB) indicating current marijuana use ≥4 days/week for ≥1 year, positive urine THC dipstick test ($> 50\text{ng/mL}$; indicating marijuana use in the past 48-72 hours), motivated to change their marijuana use (≥ 1 on a 10-point Likert-type scale), regular or sporadic use of nicotine cigarettes (> 1 cigarettes in the past 30 days), self-report of regular menstrual cycles ≥6 months (female only), willing to use double-barrier contraception if sexually active and not surgically sterilized (female only), ability to comply with study procedures, ability to provide informed consent.

Exclusion: Current breastfeeding (females only), current or planned pregnancy within the next three months (females only), DSM-IV diagnoses for psychotic disorders, bipolar disorder, ADHD, major depressive

disorder within the last 3 months, substance dependence within the last 3 months with the exception of nicotine and marijuana dependence, unstable psychotropic medications (<3 months), current use of exogenous hormones, finasteroid (propecia), efavirenz, red clover, ketoconazole and other drugs that are CYP3A4 inhibitors, conditions contraindicated to progesterone treatment (including, but not limited to, thrombophlebitis, deep vein thrombosis, pulmonary embolus, clotting or bleeding disorders, heart disease, diabetes, history of stroke, allergy to peanuts, hypersensitive to progesterone and liver dysfunction).

Visit Sequence & Procedures

Screening Visits (Visits 1 and 2): Candidates completing the consent process will be screened in a two-visit process (with the option of completing visits 1 and 2 simultaneously). For males, this two-visit process will be scheduled within two weeks of completion of the phone interview. For females, this two-visit process will be scheduled during the follicular phase of their menstrual cycle (in order to avoid any potential menstrual phase effects on marijuana use or mood measures, as well as to limit wait time for initial study procedures) (details below). Therefore, after the phone screen females will be told to contact the study coordinator with the first day of their next period, and then the two-part screening visits will be scheduled during days 1-7 (where Day 1 is the onset of menses) of the menstrual cycle.

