At the first of two screening visits (*Screening Visit 1*), the study will be described in detail to candidates by the study coordinator, and informed consent will be obtained. Subjects agreeing to participate will undergo medical, psychiatric and other evaluation to determine eligibility. The medical evaluation will include: brief physical exam (height, weight, blood pressure, heart rate, and medical history interview), psychiatric interview, carbon monoxide level and a blood draw (for measurement of serum hormone levels and liver function via ALT and AST measurement), a urine pregnancy test (females only) and a drug screening for marijuana (see *THC Urine Dipstick Test* for more information). Trained staff will conduct all interviews including the Structured Clinical Interview for DSM-IV (SCID; First, 1995) and instrument administration. Self-report instruments measuring impulsivity, personality characteristics, stress, caffeine use, tobacco use, marijuana use, craving and behavior will be completed. At the second screening visit (*Screening Visit 2*; scheduled within two days of Screening Visit 1), impulsivity tasks will be completed. The investigators will review the data to determine eligibility. Subjects meeting eligibility criteria will be given instructions on when to come back for their Baseline Visit (details below).

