Baseline Visit (Visit 3): Female subjects will be instructed to come into the clinic within three days of the start of their Luteal Phase for their baseline visit and to start medication (PRO or PBO). Female subjects will self-report menstrual cycle length at their screening visit and staff will determine when their Luteal Phase will most likely begin. Male subjects will be instructed to come into the clinic according to their assigned delay (per randomization list generated by the Statistical Analysis Core). This visit will occur seven days prior to quit date. At this visit, subjects will be randomized to PRO or PBO within strata defined by sex. The Statistical Analysis Core (SAC) will generate the randomization tables (one for each sex, 1:1 allocation using randomly permuted blocks of size 2 and 4), and the Clinical Trials Research Pharmacy will use it to determine randomization assignment. Randomization assignment will be stored in a secure file in a secure location at the Clinical Trials Research Pharmacy, to be shared only with the SAC. All other project staff including PI and study coordinator, as well as the participant, will remain blinded to the randomization assignment. At the baseline visit subjects will provide a blood sample (for hormone assessment), urine sample for THC, breath sample (to confirm smoking status via carbon monoxide breathalyzer), have their vital signs (blood pressure, heart rate, weight) measured, be informed of their quit date, and receive brief behavioral counseling to prepare for their quit date. At the end of this visit subjects will be compensated for their time, given study medication along with instructions for taking the medication (beginning at 8PM that day), as well as a clinic visit schedule for the remaining clinic visits. This visit will take approximately one hour to complete.

Marijuana Change Date Assignment: Change date (Week 0) will be set for 7 days following the Baseline Visit. Since this entails a delay of variable duration from Screening Visit 2 to Baseline Visit (thus impacting timing of medication initiation) across female subjects, each male subject will be matched to a female subject for a similar delay so that, across the male and female groups, study procedures will follow a similar chronology.

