| Marijuana: Since you last visit... (TPD - Times per day) | | MJ |
| Cigarettes: Since you last visit... (CPD) | | CPD |
| Caffeine: Since you last visit... (ozs.) | | CAFF |
| Computer Tasks: | | | | | | | | | |
| Immediate/Delayed Memory Task: Impulsivity & attention | | IMT DMT | | | | | | IMT DMT | |
| GoStop Computer Task: Response inhibition | | GoStop | | | | | | GoStop | |
| Balloon Analogue Risk Task: Risk-taking | | BART | | | | | | BART | |
| Biological Specimen Collection: | | | | | | | | | |
| Blood (plasma/serum): Hormones | BLOOD | | BLOOD | BLOOD | | BLOOD | | BLOOD | BLOOD |
| Urine: THC and Cotinine | | URINE |

Analysis Plan

Our primary outcome is change in marijuana use as defined by the TLFB at the week 4 visit relative to the baseline visit. This is a pilot study to generate data to potentially motivate and justify a future fully-powered study of PRO and marijuana cessation, so the intent of these analyses is to estimate magnitude and direction of treatment effects and associations with impulsivity (sex-specific and overall). While we expect baseline covariates to be balanced across treatment groups due to the randomization, this pilot study is small so both unadjusted and adjusted assessments of effects will be carried out by including the randomized treatment assignment and pre-specified adjusting covariates such as age, baseline progesterone, estradiol, baseline

impulsivity measures, etc. This pre-specified list will be determined by the study team during the finalization of the protocol, prior to the first study enrollment. We expect these analyses to be somewhat conservative, since they do not explicitly account for the randomized permuted blocking (Matts and Lachin, 1988). An analysis that accounts for the blocking (such as a stratified Mantel-Haenzel test) cannot be generalized to include the adjustment for impulsivity measures, for example, which are a focus of this proposal. All persons randomized and with a measured primary outcome at the week 4 visit will be included in this analysis, regardless of whether or not they ever took any of their assigned treatment (intent-to-treat analysis); persons with missed visits are discussed below.

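### The primary percent reduction divides by Baseline Visit marijuana use, for which the plan sets no minimum before randomization, no fixed recall window in its text, and no rule for a zero value

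*Combined protocol and SAP*

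**What the plan says.** **Entry.** The inclusion criteria require "self-report Timeline Follow-Back (TLFB) indicating current marijuana use ≥4 days/week for ≥1 year". Eligibility is settled after the two screening visits: "The investigators will review the data to determine eligibility".

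**Interval.** For women, "the two-part screening visits will be scheduled during days 1-7" of the cycle. Then: "Female subjects will be instructed to come into the clinic within three days of the start of their Luteal Phase for their baseline visit". Men are matched to a similar delay. Marijuana Change Date Assignment acknowledges the consequence: "Since this entails a delay of variable duration from Screening Visit 2 to Baseline Visit". No number of days is given.

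**Baseline Visit.** Urine THC is collected, and Table 1 schedules a marijuana TLFB. Randomization takes place at this visit. Neither measurement carries a minimum-use requirement.

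**Outcome.** "Our primary outcome is change in marijuana use as defined by the TLFB at the week 4 visit relative to the baseline visit". Under Addressing Hypothesis 1a, percent reduction is regressed on treatment in a linear model for each sex separately. Hypotheses 1b, 1c, 2a and 2b use the same ratio.

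**Recall window.** The marijuana row of Table 1 reads "Marijuana: Since you last visit... (TPD - Times per day". The text on study measures sets no marijuana window. It does describe the cigarette and caffeine TLFBs as covering each of the last 7 days.

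**Who is analysed.** Everyone randomized with a measured week 4 outcome is included. The missing-data plan deals only with a missing week 4 TLFB or urine THC.

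**The concern.** The criterion that guarantees a usable starting level applies at one time, and the denominator is taken at another. Between the two, people who have consented to a trial about changing their marijuana use may already have begun to change it. Under Table 1's label, the Baseline report would cover exactly that interval.

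Two things follow:

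- A participant with zero Baseline use has no percent reduction, and the plan neither excludes that person nor says what to do. Any handling would be chosen after the data are seen.
- A participant with very low Baseline use who then returns to usual use scores as a huge increase, despite having entered as a heavy user.

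The stated purpose of this pilot is to estimate the size and direction of effects, by sex and overall. In a cell of about 10, one such value can set both.

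**Working it through.** The plan gives no delay in days, no distribution of use, no SD and no power calculation, so there is no planned figure to reproduce. Everything marked assumed is illustrative.

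**1. Cell size (Study Design).** 20 per drug group, half female: 20 × 0.5 = 10 per sex-by-arm cell.

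**2. Delay.** Assume a 14-day luteal phase, so that it starts on cycle day L − 13 for cycle length L. Screening ends on day 1–7, and Baseline falls within the three days from luteal start. The delay then runs from (L − 13) − 7 to (L − 13) + 3 − 1 days.
- L = 24: 4 to 13 days
- L = 28: 8 to 17 days
- L = 35: 15 to 24 days

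The cycle lengths are assumed; the documents give no range.

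**3. Leverage of one denominator.** Percent reduction = 100 × (1 − week 4 use ÷ baseline use). Take nine participants at 50% and a tenth using 2 times/day at week 4. The cell mean is (9 × 50 + x) ÷ 10.

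| Tenth participant's baseline (times/day) | x (%) | Cell mean (%) |
|---|---|---|
| 3 | 33 | 48 |
| 0.5 | −300 | 15 |
| 0.25 | −700 | −25 |
| 1/7 | −1300 | −85 |
| 0 | undefined | undefined |

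**4. Chance of at least one affected participant among 40.** 1 − (1 − p)^40 gives 33% at p = 1%, 64% at 2.5% and 87% at 5%. The rate p is unknown.

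**5. Short windows alone.** The criterion sets days per week but no minimum times per day. Assume a once-daily user at exactly 4 days/week, with independent days. Over a 4-day window the chance of no use days is (3/7)^4 = 3.4%, and of at most one is 3.4% + 4 × (4/7) × (3/7)^3 = 21%. Over 8 days the chance of at most one is 1.3%.

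**6. Simulation of the arm difference within one sex.** Assumed: 10 per arm, no treatment effect, usual use lognormal (median 3/day, log-SD 0.5), Poisson counts, Baseline window 4–24 days, week 4 use uniform at 20–100% of the reference level shown, undefined values dropped, 20,000 runs.

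| Early behaviour | Week 4 relative to | SD (points) |
|---|---|---|
| Fixed 28-day denominator at usual use | usual use | about 14 |
| Baseline denominator, nobody cuts down | usual use | about 16 |
| 5% cut to 0–40% of usual, then rebound | usual use | about 87 |
| 10% cut to 0–40% of usual, then rebound | usual use | about 124 |
| 5% / 10% cut to 0–40%, stay reduced | reduced level | 16.9 / 18.5 |
| 10% cut to 40–80%, then rebound | usual use | about 20 |

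The large values move by several points between runs because the ratio is heavy-tailed. With 10% deep reducers, about 17% of sex strata contain at least one undefined value.

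**7. Second simulation.** This uses a fixed 7-day Baseline window and assumes week 4 use with median half of usual (log-SD 0.7), again allowing rebound. The SD is 28 with no cut-down, 33 if 5% halve their use, 51 if 5% cut by three quarters, 104 if 5% cut by 90%, and 144 if 10% cut by 90%. A 7-day denominator at screening stays at about 28. Fixing the window at 7 days before Baseline is therefore not enough on its own.

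**The case against.** The strongest reply is that instability is a possibility here, not a consequence of the plan. It needs deep cut-down and then a rebound, and the documents give a rate for neither. Participants learn their quit date and receive preparatory counseling only at the Baseline Visit, and the required motivation is only 1 or more on a 10-point scale. Both make deep cut-down beforehand less likely. TLFB and urine THC are measured at Baseline, so cases would be visible. All of this stands. It limits the expected size but does not supply a rule for zero.

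The variable window rests on a table label alone. Table 1 labels the cigarette and caffeine TLFBs in the same way, yet the text gives those 7 days. So the marijuana window is unspecified and cannot be said to be shown variable.

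A reader might also infer that the screening TLFB cannot establish the use criterion, because Screening Visit 2 is "scheduled within two days of Screening Visit 1" and a since-last-visit window would then span at most two days. The documents do not support that. The criterion itself presupposes a longer look-back, the text has marijuana use self-reported at Screening Visit 1 and the TLFB completed at every clinic visit, and the label has no natural meaning at a first assessment. What is missing is a stated look-back.

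Finally, a pre-treatment baseline is conventional. Moving the denominator wholly to screening would credit pre-randomization change as outcome and, since entry selects on heavy use, invite regression to the mean. That is a fair caution about the remedy.

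**Conclusion.** The gap is real and should be fixed. The documents themselves establish that the use criterion is applied at screening, that the denominator comes from a later visit, that no use criterion is re-applied before randomization, that no marijuana window is fixed in the text, and that a zero baseline has no handling rule although the participant must be analysed.

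The size is conditional. The SD of the arm difference of about 87–124 points, against 14–16, holds only under the assumed 5–10% of deep reducers who rebound. It is about 17–20 if they stay reduced or cut down mildly.

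Three stronger conclusions might be drawn and are not supported:

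- **That the primary outcome is unstable as planned.** No cut-down rate is given.
- **That the delay is 4 to 24 days.** That range comes from assumed cycles of 24 to 35 days.
- **That the treatment comparison is systematically biased.** Early reducers are randomized like everyone else, so the risk to Hypothesis 1a is imprecision and handling chosen after the fact. For an estimation-only pilot that is serious but not disabling.

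**What to change.** 1. Set one fixed look-back for the marijuana TLFB denominator, for example 28 days, expressed as mean times per day in the same unit as week 4. State the date on which it ends. It should be long enough to include use before screening: with a 24-day delay, a 28-day window ending at Baseline would include only 28 − 24 = 4 such days, so it would protect less than the simulated denominator, which was 28 days at usual use. State a fixed look-back for the criterion of at least 4 days per week as well.
2. State in advance how zero or very low baseline use is handled in the primary estimate.
3. At the Baseline Visit, before randomization, use the TLFB already scheduled there to flag anyone who no longer meets the use criterion. Repeat the primary estimate without flagged participants.
4. As an alternative or sensitivity analysis, model week 4 use with baseline use as a covariate (ANCOVA or a count model). This needs no division by baseline.

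**Cost.** Protocol wording and a few more minutes on one interview, with no new visits or staff. If data have already been collected, items 2 and 4 can still be fixed before unblinding, and the flag in item 3 can be derived from the recorded Baseline TLFB.

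**Downside.** A longer look-back counts some pre-randomization change as reduction. This is balanced between arms in expectation for Hypothesis 1a, but not for the non-randomized comparisons in Hypotheses 1b, 1c and 2a. For those, report the Baseline Visit denominator as a sensitivity analysis.
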